#### **IIId. Number of Subjects**

From a retrospective chart review sampling of displaced forearm fractures requiring reduction from June 1 to August 31, 2015 at CHAM, there were 20 displaced forearm fractures that underwent a closed reduction procedure in the Pediatric Emergency Department. 5 of the 20 displaced forearm fractures (25%) were inadequately reduced and required repeat reduction and/or operative management. Based on a recent study by Wellsh et al, only 6% of patients required repeat fracture reduction when US guidance was used.

In order to observe such a difference with 80% power, the sample size calculation would require a minimum of 56 patients in each group (standard of care vs US-guided reduction) with alpha set at P= 0.05.

Statistical significance will be assessed using mean, percentages, frequency distributions, and p-value. The significance will be set at 0.05. The test statistic used will be the Chi-square test. Confidence intervals will also be obtained. After the primary analysis of the group differences, logistic or normal regression will be used to determine factors related to these outcomes. The significance will be set at 0.05. The statistical approaches will be further developed with the assistance of the statistician in the orthopaedic surgery department following data collection and study approval.

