could potentially escape detection if the transducer is placed parallel to the course of the fracture. Fractures were demonstrated as either cortical discontinuities or interruptions in acoustic shadows.

Several studies in the pediatric literature have shown that ultrasound can adequately identify long bone fractures, determine the need for reduction of a displaced fracture and assess the adequacy of reduction when compared to plain films. In a prospective study involving pediatric emergency medicine (PEM) physicians by Patel et al, ultrasound was compared to plain films to identify fractures, determine need for reduction and assess adequacy of reduction. The study found a 95.5% agreement between ultrasound and radiography in fracture identification, a 92.3% agreement in need for fracture reduction and a 92.3% agreement in adequacy of reduction.

In a case study, Durston and Swartzentruber described three cases in which ultrasound was helpful in guiding fracture reduction. Chen et al, in a prospective study, compared ultrasound to x-ray for the diagnosis of forearm fractures and used ultrasound as a real-time imaging modality to guide the reduction procedure. They found 97% sensitivity and 100% specificity in the diagnosis of forearm fractures with ultrasound compared to plain films and the initial success rate of ultrasound-guided reduction was 92% with two patients requiring repeat reduction. Two of 65 fractures were missed, both ulnar styloid fractures in patients who also had radial metaphysis fractures and therefore the management was not altered because of the missed diagnosis. However, this study did not compare ultrasound-guided reduction to blinded reduction or reduction with another mode of real-time imaging such as fluoroscopy.

Of note, children tolerate musculoskeletal ultrasound, even in areas of injury, very well. Chien, et al. evaluated the use of ultrasound for the diagnosis of clavicular fractures in children and found that the ultrasound examination was not associated with an increase in pain. While not formally studied, both Patel et al and Chen et al noted that with liberal application of ultrasound transmission gel, there was no worsening of pain and patients did not require additional pain medication during the ultrasound exam^7.

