## **Ib. Objectives/Purpose of the study**

Our objective is to conduct a prospective randomized trial to assess the utility of using real-time ultrasound imaging in the reduction of forearm fractures in the PED. We also plan to assess provider satisfaction with using ultrasound for the reduction procedure compared to fracture reduction without use of ultrasound. We hypothesize that the use of ultrasound will improve patient outcomes and provider satisfaction. Thus, the primary outcome of the study will be:

- 1) To compare the number of patients requiring a repeat reduction procedure between the experimental group (ultrasound guided fracture reduction) and control group (standard of care forearm fracture reduction).

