### **Secondary Outcomes:**

- 1) To compare provider satisfaction with the reduction procedure between the two groups. Specifically, we will ask providers to determine:
  - I. Providers from experimental group:
    - a. Ease of fracture reduction - scale 1-5, (1=easy 5=very difficult)

---

Ang et al, Ultrasound-guided reduction of distal radius fractures, Am J of Emerg Med, 2010; 28, 1002-1008

Chinnock et al, Ultrasound-guided reduction of distal radius fractures, J of Emerg Med, 2011, 40 (3) 308-312

 Brahm J et al, A Randomized controlled trial of emergency department ultrasound-guided reduction of distal radius fractures, Annals of Emerg Med-Abstracts, 2011 Oct; 58(4), 230

IRB #:

Version 1.2

- b. Ease of using ultrasonography on a 5 point scale (1=easy, 5=very difficult).
- c. Was ultrasound helpful in completing the fracture reduction? a) yes b) no c) uncertain

II. Providers from control group:

- a. Ease of fracture reduction - scale 1-5, (1=easy 5=Most difficult)
- b. Do you think real-time imaging would have been helpful for this reduction?

|

- 2) To compare the adequacy of reduction between groups by measuring and comparing the degree of angulation and displacement on the post reduction x-rays. An orthopedic surgeon who is blinded to the patient's group assignment will read the x-rays. The acceptable degree of angulation will be the same in both groups. The acceptable degree of angulation based on age is less than 20 degrees' angulation for patients younger than 10 years of age and less than 10 degrees' angulation for patients older than 10 years of age.
- 3) To compare the time for the fracture reduction procedure between the experimental and control group.
- 4) To compare the number of patients requiring operative repair after reduction between the experimental and control group.
- 5) To compare the post-reduction ultrasound and x-ray interpretation, including measurement of degree of angulation and displacement on the ultrasound and x-ray for each patient.

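### The 80% power compares a control rate for repeat reduction or operation (25%) with an ultrasound rate for repeat reduction (6%), so it is not shown to apply to the primary outcome

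*Combined protocol and SAP*

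**What the plan says.** Section IIId (Number of Subjects) takes its control rate from a three-month chart review: 5 of 20 fractures (25%) "were inadequately reduced and required repeat reduction and/or operative management". Its ultrasound rate comes from a cited study in which "only 6% of patients required repeat fracture reduction when US guidance was used". On that difference, with 80% power and alpha 0.05, "the sample size calculation would require a minimum of 56 patients in each group". The test is chi-square, and "Confidence intervals will also be obtained".

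Section Ib gives the primary outcome: "To compare the number of patients requiring a repeat reduction procedure between the experimental group" and the control group. Operation is kept apart, as item 4 of the Secondary Outcomes: "To compare the number of patients requiring operative repair after reduction between the experimental and control group".

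Section IIIb (Data Collection / Monitoring) names another primary endpoint: the percentage of patients whose angulation on the post-reduction x-ray is adequate. Item 2 of the Secondary Outcomes gives the angulation limits by age.

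Section Ia (Background and Significance) reports one paediatric series in which "the initial success rate of ultrasound-guided reduction was 92% with two patients requiring repeat reduction".

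**The concern.** As worded, the two planning rates count different events. The control event takes in patients who went to operation without a second reduction; the ultrasound event does not. The control event is also broader than the primary outcome in section Ib, since the protocol lists operative repair separately. Nothing in the protocol says how many of the five control cases had a repeat reduction, and nothing gives an operative rate under ultrasound.

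The direction matters. Taking the stated rates as given, putting both arms on one definition can keep the planned difference or shrink it, but cannot widen it. Restricting the control arm to repeat reductions leaves 25% or lowers it. Extending the ultrasound arm to include operations leaves 6% or raises it.

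At stake is whether 56 per arm can answer the question. This is the trial's only power statement, and a null result could be read as coming from a trial with 80% power for repeat reduction when that has not been established.

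**Working it through.** **Inputs.** Control rate p1 = 5/20 = 0.25, ultrasound rate p2 = 0.06, 56 per arm, alpha 0.05, chi-square test (all section IIId). Sidedness is not stated; two-sided reproduces the plan's figure and is used throughout.

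**1. The plan's own figure.** With p̄ = (p1 + p2)/2, let A = √[2p̄(1 − p̄)] and B = √[p1(1 − p1) + p2(1 − p2)]. Then

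n per arm = (1.960·A + 0.842·B)² / (p1 − p2)²

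Here p̄ = 0.155, A = 0.5118, B = 0.4939, and p1 − p2 = 0.19. So n = (1.0031 + 0.4156)² / 0.0361 = 55.8, which rounds up to 56. The stated sample size is reproduced.

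**2. Power at 56 per arm.** Power = Φ{[(p1 − p2)·√56 − 1.960·A] / B}. For 25% against 6%: (1.4218 − 1.0031)/0.4939 = 0.848, and Φ(0.848) = 0.802.

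**3. If repeat reduction is the endpoint.** Hold ultrasound at 6% and vary how many of the five control cases had a repeat reduction. The splits are assumptions; the protocol gives none.

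| Had a repeat reduction | Control rate | Power, formula | Power, exact chi-square |
|---|---|---|---|
| 5 of 20 | 25% | 80.2% | 82.7% |
| 4 of 20 | 20% | 59.8% | 61.6% |
| 3 of 20 | 15% | 34.1% | 34.5% |

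With two or fewer, the control rate is 10% or less, so the planned difference is at most 4 points or points the wrong way. The exact column is for the uncorrected Pearson test.

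**4. How much slack there is.** Against 6%, the smallest control rate that gives 80% power at 56 per arm is 24.9% by the formula and 24.2% by the exact calculation. One reclassified chart moves the rate by 1/20 = 5 points, so a single operative-only case takes the power below 80% by either method.

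**5. If the composite is the endpoint.** Hold control at 25%. The ultrasound composite rate is then 6% or more. Values above 6% are assumed.

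| Ultrasound composite rate | Power, formula | Power, exact chi-square |
|---|---|---|
| 6% | 80.2% | 82.7% |
| 8% | 68.3% | 70.3% |
| 10% | 55.2% | 56.8% |

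**6. The protocol's other ultrasound figure.** The 92% initial success in section Ia implies 100% − 92% = 8% repeat reduction. Two failures at a rounded 92% mean 24 to 26 patients (22/24 = 91.7%, 24/26 = 92.3%). Set against 25%, 8% gives 68.3% power; that comparison is like for like only if all five control cases had a repeat reduction.

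**7. Precision of the control rate.** The exact (Clopper-Pearson) 95% interval for 5/20 is 8.7% to 49.1%. True power could therefore lie above 80% as well as below it, for a reason separate from the definitions.

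**8. If adequate angulation is the endpoint.** Power cannot be computed. The five control cases were those that were inadequately reduced and also had further treatment, which is not a count against the age-specific angulation limits. No ultrasound rate for angulation is given.

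**The case against.** The strongest reply is that the loss is conditional. The control wording allows all five cases to have had a repeat reduction, and then 25% against 6% matches section Ib and the 80% stands. That is correct, and it is why the finding is that the power is not shown to apply, rather than that the trial is underpowered.

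Section Ib also does not define what counts as a repeat reduction procedure, so operative reduction might have been meant to count. Listing operative repair as its own secondary outcome points to separation without proving it. If operation was intended to count, the definition should say so, and the ultrasound rate then needs the same basis. Likewise the 6% comes from a study known here only by one line; the mismatch is established for the protocol's wording, not for that study's data.

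A recount will not make the power firm. Moving from 5/20 to 4/20 changes the exact interval from 8.7%–49.1% to 5.7%–43.7%, so sampling error in 20 fractures exceeds the shift from the definition. This stands as a limit on the remedy. The two problems still differ: imprecision can go either way and needs more data to reduce, while the mismatch can only favour the plan and can be removed by looking at the records.

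Finally, a minimum sample size always sits at its target power, so having no slack is ordinary. True, but it is also why one case is enough to matter. The conflict between sections Ib and IIIb is a problem in its own right; it enters here because the power statement has to refer to one endpoint.

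**Conclusion.** The concern holds. The calculation of 56 per arm is correct for the two rates entered, but those rates are described on different events, and the 80% is not shown to apply to the primary outcome in section Ib or to the one in section IIIb. For repeat reduction, power at 56 per arm is 80%, 60% or 34% if none, one or two of the five control cases were operative only. For the composite, it is 80%, 68% or 55% if the ultrasound rate is 6%, 8% or 10%. These ranges assume a two-sided 0.05 test, the pooled formula and the stated rates otherwise taken at face value; no document favours any one scenario.

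The mismatch does not bias the treatment comparison or inflate type I error, and the planned confidence intervals would show any imprecision. It should be fixed because the 80% cannot be relied on as it stands when judging whether the sample is large enough. Confidence is high in the mismatch itself; any loss of power is possible but not shown.

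**What to change.** 1. Reconcile sections Ib and IIIb so that one primary endpoint is named.
2. If it is repeat reduction: state in section IIId how many of the five chart-review cases had one, use that rate against 6%, add the 8% implied by section Ia as a sensitivity value, and restate the power of 56 per arm.
3. If it is the composite: define it in section Ib, and give an ultrasound rate on the same composite or label it as an assumption with a range. Restate the power.
4. If it is adequate angulation: take the control rate from the x-rays of all 20 chart-review fractures, using the limits in Secondary Outcomes item 2 ("The acceptable degree of angulation based on age is less than 20 degrees" for those under 10, and a separate limit for those over 10). Age exactly 10 falls in neither group, so its handling must be stated. Give an assumed ultrasound rate with a range, and restate the power.

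Cost: the repeat-reduction route means re-reading five charts. The angulation route means re-reading up to 20 x-rays and adopting an ultrasound rate that the documents do not contain. The composite route needs no chart work for the control rate but also needs an ultrasound rate that the documents do not contain. Every route needs edits to section IIId and to section Ib or IIIb. The records are assumed to be still accessible. No added enrolment is required, though the restated power may be less favourable.

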While it has been our experience that the majority of reduction procedures performed in the PED are done without the use of any real time imaging, some orthopedic surgery residents employ the use of the c-arm (fluoroscopy) and/or a portable x-ray machine during the reduction procedure. At his/her discretion, the orthopedic resident may use either of these modalities in both the ultrasound and control group as per standard of care in the PED. The use of these modalities will be recorded.

After the reduction procedure in the ultrasound group and prior to reviewing the post reduction x-ray, the orthopedic resident will complete a brief questionnaire with the following questions.

For the experimental group:

- a. Rate the ease of fracture reduction from 1-5, (1=easy 5=Very difficult)
- b. Was ultrasound helpful in completing the fracture reduction? a) yes b) no c) uncertain
- c. Rate the ease of using ultrasonography on a 5 point scale (1- easy, 5=very difficult).

The control group will undergo fracture reduction without ultrasound guidance as per the current standard of care in the PED. After the reduction procedure in the control group, the orthopedic resident will complete a brief questionnaire with the following questions:

For the control group:

IRB #:

Version 1.2

- a. Rate the ease of fracture reduction from 1-5, (1=easy 5=very difficult)
- b. Do you think real-time imaging would have been helpful for this reduction?

After the reduction and casting is completed, patients in both groups will undergo a post-reduction x-ray. Based on the degree of displacement on the x-ray, the orthopedic surgeon will determine whether the patient needs a repeat reduction, as per routine standard of care. If a repeat reduction is required, the treating physician can choose to use ultrasound at his/her discretion. The angle of displacement will be measured on the post-reduction x-ray by an orthopedic surgeon. Additionally, the angle of displacement measured on the post-reduction ultrasound will be measured and compared to the angle of displacement on the post-reduction x-ray. An expert sonographer will review cases where the ultrasound and x-ray results do not correlate.

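### The plan does not say how several ratings from the same resident will be handled; simple confidence intervals for the two items asked only in the ultrasound arm would probably be too narrow

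*Combined protocol and SAP*

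**What the plan says.** Secondary outcome 1 is "To compare provider satisfaction with the reduction procedure between the two groups". Section IIIa makes the resident the rater: after each reduction "the orthopedic resident will complete a brief questionnaire with the following questions". Ease of reduction (1 to 5) is asked in both arms. Helpfulness of ultrasound (yes, no, uncertain) and ease of ultrasonography (1 to 5) are asked in the experimental arm only. Control-arm residents are asked instead whether real-time imaging would have helped.

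The analysis text is in the section Number of Subjects, after the sample size for repeat reduction: "The test statistic used will be the Chi-square test. Confidence intervals will also be obtained". It adds logistic or normal regression for factors related to the outcomes, and leaves further development of the methods to a statistician after data collection and study approval.

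Section IIIb lists the ultrasound experience of the physician who scans, but no code for that physician or for the rater. The documents do not state the number of residents, the procedures per resident or any cap on them. They do not mention clustering, an ICC, random effects or robust variance.

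**The concern.** The questionnaire is completed once per procedure, but the opinion belongs to the resident. Someone who finds ultrasound useful, or awkward, is likely to say so on more than one form. Fifty-six forms from a limited group of residents then carry less information about residents in general than 56 forms from 56 people. The usual binomial or t interval ignores this.

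It matters most for the two ultrasound-only items. They have no control-arm counterpart, so differences between residents cannot cancel in a comparison. At stake is how firmly the trial can say that residents find ultrasound helpful and easy to use. The protocol's hypothesis covers provider satisfaction as well as patient outcome. If no rater code is planned, a later analyst also has no designated field with which to correct the intervals.

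**Working it through.** **1. The plan's own figure.** Inputs from Number of Subjects: control rate 25%, since "5 of the 20 displaced forearm fractures (25%) were inadequately reduced and required repeat reduction and/or operative management"; ultrasound rate 6%, since "only 6% of patients required repeat fracture reduction when US guidance was used"; power 80%; alpha 0.05, sidedness not stated. With pooled variance under the null, two-sided, no continuity correction, and mean rate 0.155:

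n = [1.960 × √(2 × 0.155 × 0.845) + 0.842 × √(0.25 × 0.75 + 0.06 × 0.94)]² / 0.19² = 55.8, rounded up to 56.

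Power at 56 per group is 80.2%. The stated number reproduces, and this point does not affect it. The plan gives no precision figure for the ratings.

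**2. Are repeat raters likely?** The trial needs at least 2 × 56 = 112 procedures at one hospital. For nobody to rate twice, it would need 112 different residents, or 56 for the ultrasound-only items. This is an inference from the design; the documents do not state it.

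**3. Simple interval, taking one form per ultrasound-arm patient (56).** The plan gives no expected proportion for helpfulness. As an illustration, use the 78% reported in the background for a cited study of ultrasound and fluoroscopy in pediatric forearm fractures. The 95% half-width is 1.96 × √(0.78 × 0.22 / 56) = 10.85 percentage points.

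**4. Allowing for resident.** With J residents and equal caseloads, m = 56/J, the design effect is DE = 1 + (m − 1) × ICC, and the half-width is multiplied by √DE. J and the ICC are assumptions.

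| J | m | ICC | DE | √DE | Half-width (points) |
|---|---|---|---|---|---|
| 56 | 1.00 | any | 1.00 | 1.00 | 10.85 |
| 30 | 1.87 | 0.05 | 1.04 | 1.02 | 11.08 |
| 30 | 1.87 | 0.30 | 1.26 | 1.12 | 12.18 |
| 20 | 2.80 | 0.10 | 1.18 | 1.09 | 11.79 |
| 20 | 2.80 | 0.30 | 1.54 | 1.24 | 13.46 |
| 10 | 5.60 | 0.10 | 1.46 | 1.21 | 13.11 |
| 10 | 5.60 | 0.30 | 2.38 | 1.54 | 16.74 |
| 8 | 7.00 | 0.05 | 1.30 | 1.14 | 12.37 |
| 8 | 7.00 | 0.30 | 2.80 | 1.67 | 18.15 |

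The corners with repeat raters are √1.043 = 1.02 and √2.80 = 1.67, that is, 2% to 67% wider. The multipliers do not depend on the 78%, and they apply equally to the interval for mean ease of ultrasonography.

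**5. Uneven caseloads.** With coefficient of variation cv of caseload, DE = 1 + [(1 + cv²) × m − 1] × ICC. For J = 10, ICC 0.30 and cv 0.8, DE = 1 + (1.64 × 5.6 − 1) × 0.30 = 3.46 and √DE = 1.86, against 1.54 with equal caseloads. In a simulation with unequal caseloads (6,000 runs per setting, ICC 0.05 to 0.30), nominal 95% intervals covered the mean for residents in general 90% down to 72% of the time with 10 residents, and 93% down to 81% with 20.

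**6. The item asked in both arms.** The same simulation had residents treating patients in both arms, patients randomised individually, and no variation between residents in the effect of ultrasound. Type I error of the unadjusted comparison of means was 4.6% to 5.5%, close to nominal.

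**The case against.** The strongest reply is that the plan fixes no wrong method. The quoted sentences follow the sample size for repeat reduction, name no analysis for the questionnaire, leave the interval method open and defer development. That stands: the plan is silent and is not committed to independence. But the methods it names assume independence in their ordinary form, and a deferral until after data collection comes too late to add a field to the form.

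A second reply concerns the target. The intervals are too narrow for residents in general. For the average among the residents who took part, a simulation with 8 to 30 residents and near-equal caseloads gave Wilson coverage of 96% to 98%. The plan does not say which target it means. This also stands, and it is why the conclusion is limited to residents in general.

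Third, the ICC may be small, because helpfulness is asked about a particular reduction and may vary with the fracture. With 30 residents and ICC 0.05 the half-width changes only from 10.85 to 11.08 points.

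A reader might infer more than the documents support:

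- That the chi-square test is invalid for the ultrasound-only items. They have no control-arm counterpart, so no between-arm test applies; only their intervals are in question.
- That the between-arm comparison of ease of reduction gives false positives. Patients are randomised individually, and simulated type I error stayed near 5%.
- That residents are known to rate many procedures each. No count or caseload is given.
- That the rater could never be traced. The list in IIIb may not be exhaustive, and under VIb the physician performing the ultrasound documents consent. Reconstruction may be possible, but it is not planned.

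**Conclusion.** The point holds as a gap in the plan for two descriptive, single-arm items within a secondary outcome. If residents rate more than once and their ratings correlate, simple intervals overstate what the trial shows about residents in general. Over 8 to 30 residents, ICC 0.05 to 0.30 and equal caseloads, the intervals should be about 2% to 67% wider. At the illustrative 78%, that is 11.1 to 18.2 points either side instead of 10.85. Uneven caseloads increase this. With one rating per resident, or an ICC of zero, nothing changes. The documents cannot narrow the range, so no single figure should be quoted as the error.

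The comparison of ease of reduction remains valid; a resident term there would only add precision. The primary outcome and its sample size are not affected. This is an inexpensive improvement worth making before enrolment, and no threat to the trial's main conclusion.

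**What to change.** - Add a coded resident ID to every questionnaire in both arms, and list it among the data items in IIIb.
- Report the number of residents who rated and the ratings per resident with these results.
- State that the ultrasound-only items are meant to describe residents in general. Give their intervals by a cluster-robust method, clustered on resident, with a small-sample correction.
- Do not rely on an uncorrected percentile bootstrap of residents. In a simulation with near-equal caseloads it covered only 88% with 8 residents and 92% to 93% with 20.
- Optionally, analyse the shared ease-of-reduction item with a random intercept for resident, to gain precision.

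The cost is one field on the form, a few sentences in the analysis section, and wider intervals on secondary items. Sample size, treatment and patient burden do not change.

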### **IIIb. Data Collection / Monitoring**

The primary endpoint of the study is comparing the percentage of patients with an adequate degree of angulation on post-reduction x-rays between the experimental group and the control group. X-rays will be performed based on the PED routine standard of care.

Demographic data recorded by the study trained physician will include the patient's name, age, medical record number, date of birth, date of visit, and ultrasound experience of the study-trained physician performing the ultrasound. *The patient identifiers are necessary for patient tracking to match ultrasound findings with X-ray final readings and for clinical follow up.* Type of sedation used, length of procedure and any ultrasound data will be collected and recorded by study trained physicians. Radiographic readings will be collected by the investigators.

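### The primary chi-square is valid but leaves out age, which is recorded and probably prognostic; a pre-specified age-stratified test would protect against chance imbalance at almost no cost

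*Combined protocol and SAP*

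**What the plan says.** The analysis is set out in section IIId, Number of Subjects. It names a chi-square test at the 0.05 level and mentions no covariate or stratifier. After the primary analysis, "logistic or normal regression will be used to determine factors related to these outcomes". No factors are listed, and there is no limit on their number, no selection rule and no multiplicity control. Further development of the methods is left until after data collection.

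The sample size in the same section rests on a chart review in which "5 of the 20 displaced forearm fractures (25%) were inadequately reduced and required repeat reduction and/or operative management", and on a published study in which "only 6% of patients required repeat fracture reduction when US guidance was used". The result is "a minimum of 56 patients in each group (standard of care vs US-guided reduction").

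Age appears in four other places:

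- The second item under Secondary Outcomes defines "The acceptable degree of angulation based on age": under 20 degrees for patients younger than 10, under 10 degrees for those older than 10.
- Section IIa enrols ages 0 to 21, so both limits are in use.
- Section IIIa describes permuted blocks of 20 and states no stratification by age.
- Section IIIb lists "name, age, medical record number, date of birth, date of visit" among the recorded data.

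The documents name two primary endpoints. Section Ib makes repeat reduction primary. Section IIIb makes the percentage with adequate angulation on the post-reduction x-ray primary.

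**The concern.** The limit for acceptable angulation halves at age 10, so age is a natural candidate to predict the outcome. It is known before randomisation and already collected, yet the primary test does not use it and the randomisation is not stated to balance it. If one arm happens to receive more older patients, that imbalance enters the estimated difference with nothing to offset it.

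The one planned use of covariates is a later, open-ended regression. For the binary outcome it would have few events to work with. Because methods are to be developed after data collection, the choice between adjusted and unadjusted results could be made with the data in view.

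**Working it through.** **1. The plan's own sample size.** Inputs from section IIId, Number of Subjects: 25% versus 6%, "In order to observe such a difference with 80% power", "with alpha set at P= 0.05". Sidedness is not stated; two-sided is used here. The pooled rate is (0.25 + 0.06)/2 = 0.155.

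n = [1.96 × √(2 × 0.155 × 0.845) + 0.842 × √(0.25 × 0.75 + 0.06 × 0.94)]² / 0.19² = (1.003 + 0.416)² / 0.0361 ≈ 55.8, rounded up to 56. This matches the plan.

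**2. Expected events.** 56 × 0.25 + 56 × 0.06 = 14.0 + 3.36 = 17.36, with a 95% range of 10 to 25. If there is no treatment effect the total lies between 112 × 0.06 ≈ 7 and 112 × 0.25 = 28. At 10 events per model term, 17.36 supports 1.7 terms; at 5 per term, 3.5.

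**3. Chance age imbalance.** The age split is not in the documents. With a fraction f under 10 and simple allocation of age, the SD of the arm difference in age mix is √(2f(1 − f)/56).

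| Assumed share under 10 | SD (points) | Chance of an imbalance of 15 points or more |
|---|---|---|
| 50% | 9.4 | about 11% |
| 30% or 70% | 8.7 | about 8% |
| 20% or 80% | 7.6 | about 4% |

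**4. Effect of a 15-point imbalance on the estimate.** Assume control failure rates of 15% and 35% by band (average 25%) and ultrasound rates of 0.06/0.25 = 0.24 times these, that is 3.6% and 8.4%. The gap between bands is 20 points in the control arm and 4.8 in the ultrasound arm. Sharing the imbalance equally between arms gives 0.075 × 20 + 0.075 × 4.8 = 1.5 + 0.36 ≈ 1.9 points, against a planned difference of 19. With no treatment effect, or a constant risk difference, the gap is 20 in both arms and the shift is 0.15 × 20 = 3 points.

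**5. Average power and type I error.** Simulation with 56 per arm, a 50/50 age split and the proportional effect:

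| Assumed control rates by band | Chi-square | Age-stratified CMH, uncorrected |
|---|---|---|
| 25% / 25% (no age effect) | 82.7% | 82.2% |
| 15% / 35% | 82.7% | 83.4% |
| 10% / 40% | 82.5% | 84.7% |

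Type I error is near 5% for both tests throughout. With a continuity correction, CMH power falls to about 74–76%, below the planned 80%.

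**6. Power when an imbalance does occur.** Fix 24 versus 32 younger patients, a 14-point imbalance (8/56), with bands 15%/35%. If the ultrasound arm has more older patients, chi-square power is about 76% and CMH about 84%. With the opposite imbalance and no true effect, chi-square falsely favours ultrasound in 4.9% of trials against a nominal 2.5%, while CMH stays at 2.5%.

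**The case against.** The strongest reply is that nothing here is invalid. An unadjusted chi-square in a randomised trial holds its error rate, and chance imbalance is already counted in that rate. The conditional figures in step 6 describe particular realisations and average out over all randomisations. The gain in average power is small and becomes a slight loss if age does not matter. All of this stands, and it is why the point is minor.

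A reader might infer that age is prognostic by construction because it sets the pass limit. The documents do not support that. The limit defines adequate angulation, the endpoint in section IIIb. Repeat reduction, the primary outcome in section Ib, is decided by the orthopedic surgeon from the x-ray under routine care (section IIIa), with no stated tie to the limit. The planning rates and the 17 events concern repeat reduction, with operative management also counted in the 25%. Even for angulation, a stricter limit makes age prognostic only if older patients' angulation is not correspondingly smaller, and no failure rates by age are given. Likely prognostic is as far as one can go.

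Nor should a reader take the 3-point shift as the general figure: under a proportional effect it is 1.9.

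The objection to the regression is also partly fair. It follows the primary analysis, does not exclude age, and may cover continuous outcomes such as angulation or procedure time, to which an events limit does not apply. The complaint is mainly about missing detail.

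**Conclusion.** The point holds as a low-cost improvement. It does not show a flaw in the validity of the primary test. The documents confirm the unadjusted test, the age-dependent limit, the recorded age and the absence of stated age stratification. The benefit is protection in the roughly 4–11% of trials with an age imbalance of 15 points or more, where the estimate would move by about 1.9 points under the assumed 15%/35% rates and a proportional effect. Average power changes by about -0.5 to +2 points between no age effect and 10%/40%. The age split and the band-specific rates behind these figures are assumptions; the sample size and the 17 expected events come from the plan. For the binary outcome, an unlimited factor search is more than about 17 events can support.

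**What to change.** Two matters need settling first. The documents must assign patients aged exactly 10 to a band, since they fall under neither limit as written. They must also reconcile the two primary endpoint statements in sections Ib and IIIb. The stratified test can be used with either endpoint.

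Then, in section IIId, Number of Subjects, and before data collection ends:

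- State that the primary comparison is a Cochran-Mantel-Haenszel test without continuity correction, stratified by age band, with a stratified risk difference and 95% confidence interval. Report the unadjusted chi-square beside it.
- For the binary outcome, limit the later logistic model to arm, age band and at most one further named covariate, fitted with Firth penalisation and labelled exploratory. This limit need not apply to regression of continuous outcomes, though those covariates should be named too.

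The cost is wording only: no extra patients, no new data and no change to the randomisation. The downside is a loss of about 0.5 points of power if age turns out not to be prognostic.
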